## 2. Major protocol deviation

This will be considered the primary reason for study withdrawal if it is discovered after the first dose of study treatment (in the case of Part A) or after randomization (in the case of Part B) that the subject does not meet the enrollment criteria specified in the study protocol, or has not followed the study protocol, and that continuing the study would pose an unacceptable risk to the subject's health.

## 3. Lost to Follow-up

This will be considered the primary reason for study withdrawal if a subject fails a study visit and cannot be contacted. In this case, the fact that contact was attempted will be noted in the source documents.

## 4. Voluntary withdrawal

This will be considered the primary reason for withdrawal if the subject wishes to withdraw from the study. The reason for withdrawal, if provided, should be recorded in the eCRF.

Note: All attempts should be made to determine the underlying reason for the withdrawal and, where possible, the primary underlying reason should be recorded (ie, withdrawal due to an AE or lack of efficacy should not be recorded in the “voluntary withdrawal” category).

## 5. Study termination

This will be considered the primary reason for withdrawal if the sponsor, IRB, or regulatory authorities decide to terminate the study.

## 6. Lack of efficacy

This will be considered the primary reason for withdrawal if the expected level of efficacy is not obtained because of disease progression assessed by PSA level or evaluation of soft tissue or bone lesions by diagnostic imaging (according to the Prostate Cancer Handling Guidelines, Fourth Edition [16]), or if the decrease in serum testosterone meets any of the following criteria.

- 1) If, in Part A, serum testosterone does not drop below 50 ng/dL at 2 or more time points at least 7 days apart following treatment initiation, and it is determined as a result that the patient must be switched to some other therapy.
- 2) If, in Part B, serum testosterone does not drop below 50 ng/dL by 4 weeks after uptitration based on the uptitration criteria (see Section 8.1.3.1).
- 3) If, in Part B, serum testosterone exceeds 50 ng/dL on 2 consecutive occasions, or on 3 occasions in total, whether consecutive or not, by 9 weeks (57 days) after the start of treatment following uptitration in accordance with the uptitration guidelines (see Section 8.1.3.1).

## **7.6 Procedures for Discontinuation or Withdrawal of a Subject**

If a subject meets the criteria described in Section 7.5, the investigator will withdraw the subject from the study. Furthermore, subjects may withdraw from the study without providing a reason at any time during the study. If a subject withdraws from the study, the investigator will enter the primary reason for withdrawal in the eCRF, and will perform all procedures scheduled for the Early Termination Visit.

## 8.0 STUDY DRUG MANAGEMENT

This section contains information regarding all study drugs provided directly by the sponsor, and/or sourced by other means, that are required by the study protocol, including important sections describing the management of clinical trial material.

### 8.1 Study Drug

#### 8.1.1 Dosage Form, Manufacturing, Packaging, and Labeling

##### 8.1.1.1 Investigational Drug

(1) Investigational drug name: TAK-385

(2) Chemical name

*N*-(4-{1-(2,6-Difluorobenzyl)-5-[(dimethylamino)methyl]-1,2,3,4-tetrahydro-3-(6-methoxypyridazin-3-yl)-2,4-dioxothieno[2,3-*d*]pyrimidin-6-yl}phenyl)-*N'*-methoxyurea

[figure not shown]
(3) Dosage forms and doses

- TAK-385 40 mg tablets: Each tablet contains 40 mg as TAK-385
- TAK-385 80 mg tablets: Each tablet contains 80 mg as TAK-385

There are two types of study drug, described above; both are light red, film-coated tablets.

(4) Packaging and labeling

Each dosage form comes packaged 40 tablets to a bottle. The label clearly states that the drug is for use in a clinical study, and also bears the drug name, protocol number, name and address of the study sponsor (or company that manufactured the drug), manufacturing number, and storage method ([Figure 8.a](#)).

**Figure 8.a Sample TAK-385 Bottle Label**

#### 8.1.1.2 Drugs not Provided by the Study Sponsor

No drugs will be provided other than the study drug and drugs such as GnRH agonists and/or GnRH antagonists following the completion (or discontinuation) of TAK-385 administration.

#### 8.1.2 Storage

TAK-385 will be stored at room temperature (1-30°C).

Investigational drug must be stored in an appropriate, limited-access, secure place until they are used or until they are returned to the sponsor or a designee for destruction.

Investigational drug must be stored under the conditions specified on the label, and must remain in their original containers until dispensed. The daily temperature log of the drug storage area must be maintained every working day.

#### 8.1.3 Dose and Regimen

Table 8.a shows the dosage and number of tablets in Part A (by cohort), and Table 8.b shows the dosage and number of tablets in Part B (by treatment group).

**Table 8.a Cohorts, Dosages, and Numbers of Tablets (Part A)**

Cohort	Dosage/Number of Tablets
1	TAK-385 320 mg (Day 1): Four 80 mg tablets per day TAK-385 80 mg (Days 2 to 28): One 80 mg tablet per day
2	TAK-385 320 mg (Day 1): Four 80 mg tablets per day TAK-385 120 mg (Days 2 to 28): One 80 mg tablet and one 40 mg tablet per day
3	TAK-385 320 mg (Day 1): Four 80 mg tablets per day TAK-385 160 mg (Days 2 to 28): One 80 mg tablet and two 40 mg tablets per day
4	TAK-385 360 mg (Day 1): Three 80 mg tablets and three 40 mg tablet per day TAK-385 120 mg (Days 2 to 28): One 80 mg tablet and one 40 mg tablet per day
Additional cohort *1	TAK-385 320 mg (Day 1): Four 80 mg tablets per day TAK-385 40 mg (Days 2 to 28): One 40 mg tablet per day

\*1: Added if tolerability is not confirmed in Cohort 2

**Table 8.b Treatment Groups, Dosages, and Numbers of Tablets (Part B)**

Treatment Group	Dosage/Number of Tablets
80 mg	TAK-385 320 mg (Day 1): Four 80 mg tablets per day TAK-385 80 mg (Day 2 to Week 48 *3 ): Two 40 mg tablets per day
120 mg	TAK-385 320 mg (Day 1): Four 80 mg tablets per day TAK-385 120 mg (Day 2 to Week 48 *3 ): One 80 mg tablet and one 40 mg tablet per day
40 mg *2	TAK-385 320 mg (Day 1): Four 80 mg tablets per day TAK-385 40 mg (Day 2 to Week 48 *3 ): One 40 mg tablet per day
At up titration	One TAK-385 40 mg tablet per day will be added

\*2: If no problems with tolerability are found in the additional cohort in Part A

\*3: Treatment may be continued for up to 96 weeks in total

The specified dose of TAK-385 will be taken once a day orally with 1 cup of water at least 30 minutes before breakfast. Except for when various tests are being performed or an AE occurs, an effort will be made to ensure that subjects rest for 2 hours after receiving the dose.

The investigator or study support staff will check to make sure that all specified study drug has been taken.

#### 8.1.3.1 Criteria for Upward Dose Adjustments

Part A: The dose of TAK-385 will not be increased even if inadequate testosterone suppression occurs (< 50 ng/dL). If after treatment initiation the serum testosterone level does not drop below 50 ng/dL at 2 or more time points separated by at least 7 days and the investigator or sub-investigator determines that the patient needs to be switched to some other treatment, then TAK-385 treatment will be stopped and the patient withdrawn from the study.

**CONFIDENTIAL**

Part B: If the following conditions are met, the dose may be adjusted, taking efficacy and safety into consideration. Dose adjustment will be performed when the subject is examined by the investigator or sub-investigator.

If the serum testosterone level in an individual patient exceeds 50 ng/dL at Week 5 (Day 29), Week 9 (Day 57), or Week 13 (Day 85), following review of compliance, a one-time upward dose modification (increment of 40 mg daily) will be allowed. After Week 13, the dose will not be increased even if the serum testosterone level exceeds 50 ng/dL.

The dose will not be increased in the 120 mg group before the DLT evaluations have been completed for Cohort 3 in Part A, or if the dose has not been found to be tolerable. Similarly, if tolerability is not found in Cohort 2 in Part A and a 40 mg group is therefore going to be used instead of a 120 mg group, then the dose in the 80 mg group will not be increased.

#### 8.1.3.2 Criteria for Dose Holds and Dose Reduction

Part A: If a treatment-related AE occurs, or if it would be difficult to continue with TAK-385 treatment, then the dose of TAK-385 will not be reduced, and study treatment will be interrupted if necessary.

Part B: If a treatment-related AE occurs or if it would be difficult to continue with TAK-385 treatment, then study treatment will be interrupted if necessary. Subjects who experience serious AEs requiring study treatment interruption within 12 weeks (84 days) following treatment initiation may have their doses reduced by one dose level – 40 mg – following a 2-week treatment interruption period. If the AE continues even after dose reduction, or the subject's serum testosterone level exceeds 50 ng/dL for 4 to 6 weeks following dose reduction, then TAK-385 treatment will be discontinued so that the subject may receive some other therapy. If a serious AE requiring study treatment interruption occurs on or after Week 13 (Day 85) following treatment initiation, and the subject's treatment has not been interrupted prior to that, then the subject's treatment may be interrupted for 2 weeks and then resumed. However, if the AE recurs following study treatment resumption, or if the AE does not resolve even after 2 weeks of treatment interruption, then the subject will be withdrawn from the study.

Even if the dose has been increased in accordance with Section 8.1.3.1, when reducing the dose, it will be reduced by one dose level. Dose reduction will not be performed for subjects in the 40 mg group. In addition, if the dose is reduced in accordance with this section, then the dose may not be increased as described in Section 8.1.3.1.

Furthermore, if a LFT abnormality is found, it will be handled as shown in [Table 8.c](#).

**Table 8.c Guidelines for Handling Liver Function Test Abnormalities**

Category	ALT, AST, and Total Bilirubin	Study Drug	ALT and AST Tests	Treatment Interruption	Dose Adjustment
A	ALT or AST $\geq 1.5 \times$ ULN to $< 3 \times$ ULN AND Total bilirubin $< 1.5 \times$ ULN	Continue without changing the dose	Perform tests every week for 2 weeks, and then every 2 weeks for 4 weeks until stable *1	Not necessary	Not necessary
B	ALT or AST $\geq 3 \times$ ULN to $< 5 \times$ ULN AND Total bilirubin $< 1.5 \times$ ULN	Continue without changing the dose	Perform tests every week, and then every 2 weeks for 4 weeks until stable *1	Not necessary	Not necessary
C	ALT or AST $\geq 5 \times$ ULN to $< 8 \times$ ULN AND Total bilirubin $< 1.5 \times$ ULN	Interrupt treatment	Perform 2 tests in the first week, then every week for 2 weeks, and then every 2 weeks until stable *1	Interrupt treatment until stable *1	Reduce the TAK-385 dose to 40 mg
D	ALT or AST $\geq 8 \times$ ULN to $< 20 \times$ ULN AND Total bilirubin $< 1.5 \times$ ULN	Interrupt treatment	Perform 2 tests a week for the first 2 weeks, and then every 2 weeks until stable *1	Interrupt treatment until stable *1	Reduce the TAK-385 dose to 40 mg *2
E	ALT or AST $\geq 3 \times$ ULN AND Total bilirubin $> 2 \times$ ULN (Hy's law)	Permanently discontinue treatment	Perform 2 tests a week until the test values drop, and then every week until stable *1	N/A	N/A

\*1: Stable means ALT and AST both CTCAE Grade 1 ( $> ULN$  to  $3 \times ULN$ )

\*2: The study sponsor should be consulted before resuming treatment.

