#### 10.1.5.1 Liver Function Test Abnormalities

LFT abnormalities were identified as specific AEs because nonclinical studies in monkeys revealed LFT abnormalities and because clinical studies on oral GnRH antagonists with the same backbone structure as TAK-385 have revealed elevated AST and ALT as common treatment-related AEs.

The management of LFT abnormality AEs is presented in Table 8.c of the protocol. When ALT or AST levels are  $> 3 \times$  ULN, retesting will be performed within 48 to 72 hours (within 7 days at the latest). As soon as they become aware that ALT or AST levels are  $> 3 \times$  ULN, investigators will discuss detailed information on affected subjects and other potential causes with the sponsor to review whether the administration of study drug should be discontinued immediately.

If ALT or AST levels are  $> 3 \times$  ULN and total bilirubin levels are  $> 2 \times$  ULN or the PT-INR is  $> 1.5$ , and investigators conclude that the levels cannot be explained by any factor other than study drug based on the results of retesting, then they will be handled as serious AEs.

When LFT abnormalities correspond to the criteria in Section 7.5, investigators will immediately discontinue administration of study drug and will perform appropriate follow-up.

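### Table 8.c on liver tests conflicts with the dose-reduction rules of Section 8.1.3.2, has no row for ALT/AST ≥ 20 × ULN unless bilirubin is > 2 × ULN, and the liver DLT clause can be read two ways

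*Protocol*

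**What the plan says.** References are to the current protocol (Amendment 2) unless the SAP is named.

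- **8.1.3.2, Part A.** If a treatment-related AE occurs or treatment is hard to continue, "the dose of TAK-385 will not be reduced, and study treatment will be interrupted if necessary".
- **8.1.3.2, Part B.** Subjects with a serious AE needing interruption in the first 12 weeks "may have their doses reduced by one dose level", and a level is 40 mg. Up-titration does not change this: "when reducing the dose, it will be reduced by one dose level".
- **8.1.3.2, last sentence.** "Furthermore, if a LFT abnormality is found, it will be handled as shown in" Table 8.c. Section 10.1.5.1 repeats the referral: "The management of LFT abnormality AEs is presented in Table 8.c of the protocol". Neither sentence names a Part.
- **Table 8.c.** Rows A and B continue treatment. Rows C (5 to < 8 × ULN) and D (8 to < 20 × ULN) interrupt until ALT and AST are both Grade 1, printed as up to 3 × ULN, and then say "Reduce the TAK-385 dose to 40 mg". Rows A to D all require bilirubin < 1.5 × ULN. Row E (≥ 3 × ULN with bilirubin > 2 × ULN) discontinues permanently.
- **6.1.2.1.** A DLT is a related AE in the first 28 days that meets a listed criterion. The first criterion is Grade 3 or higher. Laboratory values need confirmation at least 7 days apart, with an exception that names ALT/AST > 3 × ULN, bilirubin > 2 × ULN or PT-INR > 1.5 at two time points at least 2 days apart. Section 7.5 withdraws a Part A subject who has a DLT.
- **6.1.2.3 and the SAP glossary.** A subject without a DLT is evaluable after 23 doses with observations complete. Part A is analysed by assigned cohort.

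**The concern.** Liver abnormality is the only special-interest event the protocol names, and its handling rests on rules that do not fit together. Four things follow.

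(a) A Part A site that follows the table can lower a dose that the text above the table says is not to be lowered. Because evaluability counts doses and not milligrams, that subject can then stand as evidence that the full cohort dose was tolerated.

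(b) A Part B site has two candidate step sizes. The choice matters for suppression: Section 4.1.2.5 reports that 40 mg once daily did not maintain castration levels between Days 14 and 28, and that 80 mg or above was the likely minimal fully effective dose.

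(c) The highest ALT/AST band has no table action when bilirubin is ≤ 2 × ULN, although the band below it must be interrupted.

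(d) The liver DLT clause feeds a Part A primary endpoint and the advancement rule in Table 6.c, so its threshold should be fixed in advance.

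**Working it through.** The plan's own figure on this point is the 23-dose minimum. 0.80 × 28 = 22.4, rounded up to 23, so it reproduces. A subject may miss 28 − 23 = 5 doses and stay evaluable.

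**(a) Part A, worked case.** The laboratory visit is Day 7 (Appendix A). Assume a related ALT of 6 × ULN with bilirubin < 1.5 × ULN, known before the Day 7 dose. Row C applies and treatment is interrupted. Assume the retest on Day 10 (72 hours later, inside the window in 9.1.8) is ≤ 3 × ULN. The value is unconfirmed, so it is not a DLT on either reading in (d). Under Table 8.c the subject resumes at 40 mg:

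- doses before interruption: Days 1 to 6 = 6
- doses missed: Days 7 to 9 = 3
- doses at 40 mg: Days 10 to 28 = 19
- total: 6 + 19 = 25, which is ≥ 23

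He is DLT-evaluable at the cohort dose, with 19 of 25 doses taken at 40 mg. Under the Part A sentence of 8.1.3.2 he could not have been reduced.

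**(b) Part B, dose after reduction.** Possible doses come from 8.1.3 and the single +40 mg step in 8.1.3.1.

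| Current dose | By one level | Table 8.c | Difference |
|---|---|---|---|
| 80 mg | 80 − 40 = 40 | 40 | 0 |
| 120 mg | 120 − 40 = 80 | 40 | 40 mg |
| 160 mg | 160 − 40 = 120 | 40 | 80 mg |

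**(c) Row coverage of Table 8.c** (all values × ULN).

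| ALT/AST | Bilirubin < 1.5 | Bilirubin 1.5 to 2 | Bilirubin > 2 |
|---|---|---|---|
| 1.5 to < 3 | A | none | none |
| 3 to < 5 | B | none | E |
| 5 to < 8 | C | none | E |
| 8 to < 20 | D | none | E |
| ≥ 20 | none | none | E |

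ALT at 15 × ULN with bilirubin < 1.5 × ULN must be interrupted. ALT at 25 × ULN with the same bilirubin has no row. The middle column is also empty, but exclusion criterion 21 bars bilirubin only at ≥ 2 × ULN, so a man may enrol already in that column.

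**(d) DLT clause.** Take a related ALT just above 3 × ULN on both the first test and the retest. Table 8.c prints Grade 1 as ending at 3 × ULN, so this value is just past Grade 1 and below Grade 3. The retest in 9.1.8 falls at 48 to 72 hours, that is 2 to 3 days, which matches the 2-day interval.

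- *Reading 1:* the named thresholds are themselves DLTs. The subject has a DLT and is withdrawn under 7.5, although row B says to continue.
- *Reading 2:* only Grade 3 or higher counts, and the exception merely shortens the interval. He has no DLT and continues.

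In Table 6.c one such subject moves a cohort from 0/3 to 1/3 (3 subjects are added) or from 1/3 to 2/3. At 2/3, Cohort 1 stops. Cohort 2 leads to the 40 mg cohort and, if that is tolerated, Part B compares 80 with 40 mg instead of 80 with 120 mg. All of this is subject to SMC consultation.

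The documents give no DLT rate. For assumed per-subject rates q, the chance that a cohort passes on the table alone is (1 − q)³ + 3q(1 − q)⁵: 0.973 at q = 5%, 0.906 at 10%, 0.709 at 20% and 0.494 at 30%. These only show how a wider DLT definition would act.

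**The case against.** The strongest reply is that the conflicts are smaller than they look and that other rules catch the cases.

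On (a), a related, confirmed row C or D value is a DLT on the first reading and ends in withdrawal, so no reduction arises. What remains must fall from ≥ 5 to ≤ 3 × ULN with at most 5 doses missed. In doubtful cases 6.1.2.1 also sends to the SMC the question of whether the subject belongs in the DLT analysis set. The SAP summarises reductions for Part B (2.3.1) but only holds for Part A (1.3.1), so Part B was probably meant. This narrows the point but does not remove it, because the protocol text a site follows sets no such limit.

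On (b), the permission to reduce by one level is written for serious AEs in the first 12 weeks, so most row C or D cases reach a reduction only through the table, which then supplies the dose. A fixed 40 mg may be a deliberate and more cautious liver rule. That is plausible. The example dosing patterns in SAP 2.3.2 include 120/80 and not 120/40, but they are labelled as examples and settle nothing. What stands is that no text states precedence.

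On (c), ALT/AST > 3 × ULN always triggers a retest (9.1.8), a 24-hour report (10.2.1.3) and a discussion "with the sponsor to review whether the administration of study drug should be discontinued immediately" (10.1.5.1). Section 7.5 still governs when bilirubin or PT-INR is also raised: "When LFT abnormalities correspond to the criteria in Section 7.5, investigators will immediately discontinue administration of study drug". This stands in full. The gap is a missing set action in the table, not an absence of oversight.

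On (d), the SMC decides doubtful DLTs under separate procedures that are not in these documents. That resolves cases one at a time but does not define a primary-endpoint criterion beforehand.

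**Conclusion.** The point holds and should be fixed. Section 8.1.3.2 and Table 8.c state conflicting rules for Part A, without precedence. The effect on the DLT readout is confined to non-DLT row C or D values that settle within the 5-dose allowance, and the SMC may still exclude such a subject. In Part B the discrepancy is 0, 40 or 80 mg from 80, 120 or 160 mg. The table lacks a row for ALT/AST ≥ 20 × ULN at bilirubin ≤ 2 × ULN. The two DLT readings part only for related, confirmed values below Grade 3.

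Four stronger conclusions might be inferred, and the documents support none of them:

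- That every Part A liver abnormality meets opposite instructions. Related, confirmed row C or D values lead to withdrawal on the first reading of the DLT clause.
- That reducing to 40 mg in Part B is an error. It may be an intended override, and one level would be the less cautious choice: from 160 mg it resumes at 120 mg where the table gives 40 mg.
- That ALT/AST ≥ 20 × ULN goes unmanaged. Retest, report and sponsor review all apply.
- That every subject above 3 × ULN has an uncertain DLT status. Unrelated or unconfirmed values are not DLTs on either reading, and related, confirmed Grade 3 values are DLTs on both.

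No event rate is claimed. The worked case assumes the laboratory values shown and a result available before the Day 7 dose.

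**What to change.** 1. Mark the dose-adjustment column of Table 8.c as Part B only. For Part A write: no reduction; interrupt; withdraw if a DLT or a Section 7.5 criterion is met.
2. State in 8.1.3.2 that in Part B Table 8.c sets the reduced dose for liver abnormalities (to 40 mg) and overrides the one-level rule, unless the medical lead confirms that one level was meant.
3. Add a row for ALT/AST ≥ 20 × ULN at bilirubin ≤ 2 × ULN with permanent discontinuation, or at least the row D action.
4. Add a footnote that Section 7.5 (including PT-INR > 1.5) and Part A withdrawal for a DLT override the table.
5. Make the liver DLT its own numbered criterion in 6.1.2.1, with the threshold confirmed by the medical lead.

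Do not add a blanket interruption rule for bilirubin 1.5 to 2 × ULN, because subjects may enrol in that range. Any such row needs a baseline allowance and is for the medical lead to set.

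**Cost:** a further protocol amendment, with medical confirmation of items 2, 3 and 5. If confirmed ALT/AST > 3 × ULN is adopted as a DLT, a cohort could grow from 3 to 6 subjects, which Table 6.c already allows. A Part A subject discontinued under item 3 for a value that is not a DLT would be replaced, as 6.1.2.1 already provides.

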#### 8.1.4 Overdose

An overdose is defined as a known deliberate or accidental administration of investigational drug, to or by a study subject, at a dose above that which is assigned to that individual subject according to the study protocol.

All cases of overdose (with or without associated AEs) will be documented on an Overdose page of the eCRF, in order to capture this important safety information consistently in the database. Cases of overdose without manifested signs or symptoms are not considered AEs. AEs associated with an overdose will be documented on AE CRF(s) according to Section 10.0.

Serious AEs associated with overdose should be reported according to the procedures outlined in Section 10.2.2.

In the event of a study drug overdose, the investigator will treat the subject symptomatically.

